TITLE: Efficacy of Web-Based Social-Cognitive Interventions in Right Hemisphere Stroke and Frontotemporal Dementia

NCT02506036

PI: [name]

DATE: 07/27/2015

Date: 07/27/2015

Principal Investigator: [name]

Application Number: IRB00061812

JHM IRB - eForm A – Protocol

- **Use the section headings to write the JHM IRB eForm A, inserting the appropriate material in each. If a section is not applicable, leave heading in and insert N/A.**
- **When submitting JHM IRB eForm A (new or revised), enter the date submitted to the field at the top of JHM IRB eForm A.**

1. Abstract

- a. Provide no more than a one page research abstract briefly stating the problem, the research hypothesis, and the importance of the research.

We have been studying the neural and behavioral correlates of language and other cognitive functions longitudinally in patients with stroke from the acute stage to approximately one year after stroke. fMRI and MRI scans in conjunction with behavioral data have allowed us to gain insight on some of the neural dynamics of recovery and factors that may impact or predict that recovery. We have identified important deficits in social cognitive function in individuals with right hemisphere stroke, including impaired recognition of emotion from tone of voice and facial recognition, and loss of empathy. We have identified very similar impairments in individuals with frontotemporal dementia. While we are currently testing transcranial direct-current stimulation with language therapy as a method for treating language deficits in patients with left hemisphere stroke, we have not previously attempted to treat social cognitive deficits following right hemisphere stroke and frontotemporal dementia (FTD). We now aim to use an web-based social-cognitive training program developed by Posit Science Inc. to treat empathic deficits in patients whose social-emotional functioning has been affected by stroke.

The proposed study utilizes the PI's experience in speech-language pathology and cognitive neuropsychology, clinical training in neurology, and expertise in dementia to test the effectiveness of web-based social-cognitive training organizations in FTD and right hemisphere stroke. The investigation will focus on characterizing each individual patient's deficits and determining whether cognitive training improves their performance on social-cognitive tasks. The training follows a drill-and-practice bottom-up model that uses principles of neuroplasticity to build and strengthen empathic skills such as prosody identification and facial expression recognition. The design is a cross-over trial, with randomized order of conditions; each participant will serve as their own control. Every participant will engage in both a social-cognitive training condition and a non-specific control training condition in a random order. They will be assessed at baseline, after completing one condition, and after completing the second condition. We hope to identify specific social cognition domains that are influenced by treatment and to characterize what types of patients (e.g. based on lesion location or severity of disease progression) who can benefit from these exercises.

The importance of the results is to provide a potentially effective and low cost treatment for social-emotional impairments in patients with FTD and stroke. Currently there are almost no interventions available for these symptoms in these populations, and if this treatment proves to be effective, it could have major clinical implications for the prognosis and functional outcome

of patients with stroke or FTD. The scientific impact of these results could provide greater understanding of the brain's ability to reorganize and repair damaged empathic networks in the context of training. This mode of training has not been attempted in FTD previously and previous studies of training platforms have primarily focused on language or non-social deficits in stroke. This study will be one of the first in this domain and will elucidate the nature and malleability of the social-emotional impairments in stroke and FTD.

2. Objectives (include all primary and secondary objectives)

1. Test the hypothesis that patients with right hemisphere stroke and frontotemporal dementia (FTD) show more improvement on untrained tests of social cognition after web-based social-cognitive training exercises (Posit Science Inc.) than after non-specific cognitive training.
2. Evaluate patients with FTD and stroke in multiple domains of social cognition (such as emotional contagion, affective perspective-taking, and affective prosody identification) as well as mood, attention, and working memory, before and after intervention to identify which functions improve after training.
3. Assess the feasibility and acceptability of web-based interventions in patients with stroke or FTD through examination of usage data and patient feedback.
4. Determine the effects of location of lesion or focal atrophy on improvements in social-cognitive training exercises with intervention.

3. Background (briefly describe pre-clinical and clinical data, current experience with procedures, drug or device, and any other relevant information to justify the research)

Problem: Both patients with stroke or FTD can experience impairments in social-emotional functioning. While the profile of deficits may differ in these two illnesses, there are convergent issues in empathic abilities especially in right hemisphere stroke and behavioral variant FTD. Deficits or deterioration in empathy can impact patients' interpersonal relationships and adversely impact patients' quality of life. However, there are currently very few treatments that specifically target these issues, and many of them are limited in their scope and effectiveness. Recently, web-based training interventions have shown efficacy in treating functional impairments in stroke and social deficits in other disorders such as schizophrenia. It is crucial to test whether this cost-effective and mobile intervention can be effectively utilized to treat social-emotional deficits in patients with stroke or FTD.

4. Study Procedures

- a. Study design, including the sequence and timing of study procedures (distinguish research procedures from those that are part of routine care).

Based on medical chart review, all patients will first be screened for eligibility. Patients will only be enrolled in the study if they meet both inclusion and exclusion criteria. The study will be explained to the patient and informed consent will be obtained before they undergo baseline social and cognitive assessments and receive a laptop to begin either a social-cognitive or control training condition (randomly determined by selecting one of 30 sealed envelopes).

Following the completion of the 20-30 hours of training over the course of 4 weeks, the patient will be assessed with the same measurements again. The patient will then complete the second training condition (20-30 hours over 4 weeks) that they were not randomly assigned to initially. The patient will then receive a final assessment, return the laptop, and receive compensation for the study.

Each of the three assessments will include the following tests: 1) Star Cancellation test, an assessment of spatial attention (Friedman, 1992); 2) Interpersonal Reactivity Index (IRI), a subjective evaluation of 4 components of empathy, rated by the caregiver (Davis, 1983); 3) Reading the Mind in the Eyes Test (RMET), an objective evaluation of empathy (Baron-Cohen

et al., 2001); 4) Social Cognitive Tasks from the University of Pennsylvania Computerized Neurocognitive Battery (Penn CNB), a measure of affect perception and facial memory (Gur et al., 2010); 5) Prosody Battery, a well-validated test of expression and production of prosody (Ross and Monnot, 2008; Ross et al., 1997); 6) Forward and Backward Digit Span, a brief assessment of attention and working memory; 7) Faux Pas Test, a test of social awareness (Gregory et al., 2002); and 8) the Patient Health Questionnaire-9, a well-validated screening tool for depression (Kroenke et al., 2001). The IRI must be completed by a caregiver or spouse.

b. Study duration and number of study visits required of research participants.

The study duration is around 8 weeks for each participant and will require 3 total participant visits for the baseline, 1st post-treatment (1st condition), and 2nd post-treatment (2nd condition) assessments. If there are technical issues with the laptop or online portal, assistance will be provided remotely if possible.

c. Blinding, including justification for blinding or not blinding the trial, if applicable.

Double-blinding is not possible in this study due to the large difference in the training content between the two training conditions.

d. Justification of why participants will not receive routine care or will have current therapy stopped.

Participants will receive their routine care, medications, or therapies while enrolling in this study. Cognitive rehabilitation for chronic right hemisphere stroke and behavioral variant FTD is very rare, so we anticipate most patients will be receiving no specific therapy for the deficits being targeted.

e. Justification for inclusion of a placebo or non-treatment group.

There is no placebo or non-treatment group in this study. There is a control condition (non-specific cognitive exercises) that we expect may improve general attention, but we do not expect such training to affect social cognition.

f. Definition of treatment failure or participant removal criteria.

N/A.

g. Description of what happens to participants receiving therapy when study ends or if a participant's participation in the study ends prematurely.

Participating in this current study is independent of their routine medical care. Therefore, if they prematurely end participation in the study or complete the study, patients will still continue their standard care.

5. Inclusion/Exclusion Criteria

Inclusion criteria:

1. Clinical diagnosis of right hemispheric stroke or behavioral variant frontotemporal dementia.
2. Able to give informed consent.
3. Premorbid proficiency in English (by self-report).
4. Age 18 or older.
5. Score of 21 or higher on the mini-mental state examination.

Exclusion criteria:

1. Prior history of neurological disease affecting the brain other than stroke or frontotemporal dementia (e.g., brain tumor, multiple sclerosis, traumatic brain injury)
2. Known uncorrected hearing loss
3. Known uncorrected vision loss
4. Prior history of severe psychiatric illness, developmental disorders, or mental retardation (e.g., schizophrenia, autism spectrum disorders).
5. Score of 20 or lower on the mini-mental state examination.

6. Drugs/ Substances/ Devices

- a. The rationale for choosing the drug and dose or for choosing the device to be used. N/A, no drugs to be used.
- b. Justification and safety information if FDA approved drugs will be administered for non-FDA approved indications or if doses or routes of administration or participant populations are changed. N/A
- c. Justification and safety information if non-FDA approved drugs without an IND will be administered. N/A

7. Study Statistics

- a. Primary outcome variable.

Change in performance from baseline to 1st post treatment on Penn CNB tasks (Total) vs. 1st post-treatment (new baseline) to 2nd post-treatment on Penn CNB tasks (total).

- b. Secondary outcome variables.

Changes in total and subtest scores on IRI, Prosody Battery, RMET, Faux Pas Test, and star cancellation.

- c. Statistical plan including sample size justification and interim data analysis.

We will compare the change in means of outcome measures after social cognition treatment vs. control treatment. The primary outcome variable will be change in performance on the Penn CNB tasks after the end of each treatment. The null hypothesis is $H_0: \mu_1 = \mu_2$, where μ_1 is the mean change in performance on the Penn CNB tasks between pre-treatment and post-treatment with social cognition treatment and μ_2 is the mean performance on the Penn CNB tasks between pre-treatment and post-treatment with control treatment.

Analyses. In a cross-over trial, it is essential to evaluate the effect of condition versus the effect of sequence of the treatment, and to evaluate for carry-over from one treatment to the next. Based on our clinical experience we expect little change in the Penn CNB with the control (non-specific cognitive exercises) in chronic right hemisphere stroke (as we see decline rather than recovery in chronic stroke in these functions), and little change or decline in patients with behavioral variant FTD. But we will evaluate the effect of condition versus sequence independently. The primary analyses will evaluate the change in performance on Penn CNB as the dependent variable, $Y_{ij} = \mu + S_i + \mu_{(j)} + C_{(j)} + e_{ij}$ where i represents a subjects, j represents the sequence (1 or 2). The Y_{ij} is the change in the evaluations. The S_i represents the random effect of the subjects. The $\mu_{(j)}$ represents the means of the two treatments (social cognition or control). The $C_{(j)}$ represents the carryover effects. The test for the treatment effect can be obtained from this model. Firstly, the effect of carryover effects will be tested at $p < 0.1$. If this is significant, then only the first sequence data will be analyzed as this sequence is free of carryover effects. A similar analysis will be done for the change in accuracy of secondary outcome variables.

Power. We expect to enroll up to 50 patients in the study, and expect 20-30 participants will complete the study. Because of the social cognitive deficits in these patients (accompanied by relatively low insight and motivation), there is likely to be high attrition. If the sample size in each treatment group is 13, (a total sample size of 26) a crossover design will have 86% power to detect a difference in means of 6 (the difference between treatment mean change in accuracy, μ_1 , of 10 and a control mean change in accuracy, μ_2 , of 4) using a two group t -test with a two-sided alpha of 0.05.

- d. Early stopping rules.

Patients will be allowed to stop at any time, but they will not receive compensation if they fail to complete all criteria for compensation. Their data will only be used for Aim 1 if they complete the entire study. We may be able to use data from participants who complete the social-cognition treatment condition only for Aims 2 and 3.

8. Risks

- a. Medical risks, listing all procedures, their major and minor risks and expected frequency. There are no known risks associated with the training software, use of a laptop computer, or the assessments used in this study. Participants could become bored, anxious, or embarrassed during assessment of cognitive function.
- b. Steps taken to minimize the risks. The participant will be able to stop participation at any time if they experience any issues with the use of the training software or assessments of social abilities.
- c. Plan for reporting unanticipated problems or study deviations. The PI will report unanticipated problems or study deviations to the IRB immediately.
- d. Legal risks such as the risks that would be associated with breach of confidentiality. Results of cognitive training and assessment measures will be kept strictly confidential and only the investigators participating in this study will have access to these records. If the patient wishes to know the results, or wishes to have them sent to one or more care providers, the results will be made available. If we identify any problems in thinking skills, the patient will be given the option of referral to rehabilitation specialists after the treatment study. If we identify depression (a score of 10 on the PHQ-9 or a score >0 on item 9, regarding suicidal thoughts, we will refer the patient for evaluation and treatment of depression if they are not already receiving treatment for depression. There is a small risk of breach of confidentiality, resulting in information about cognitive deficits or diagnosis being disclosed to individuals who are not care providers. There are no known legal risks, although such a breach in confidentiality might affect the person's employment. The only people who will know the patients are in a research study and will see the information about patients are members of the research team. Patients will be assigned codes for data collection and analysis. Data will be kept in locked file cabinets or secure computers that are password protected. When the study is over and the results are public, no information linked to the patient will be included. We will not collect sensitive information.
- e. Financial risks to the participants. All costs of study procedure and training modules will be provided to the patient for free at no cost to the patient or his/her insurance company.

9. Benefits

- a. Description of the probable benefits for the participant and for society.
- b. Individual participant. The study might improve a participant's cognitive and social-emotional functioning if the training is effective. The participant will also receive a small financial compensation if they complete the study (see below).
- c. Society. The results of this work may provide a novel treatment option in right hemisphere stroke and behavioral variant frontotemporal dementia and allow for future development of further interventions that target social-emotional deficits in right hemisphere stroke and behavioral variant frontotemporal dementia. Identifying a cost-effective treatment intervention will also contribute to the overall care of stroke patients.

10. Payment and Remuneration

- a. Detail compensation for participants including possible total compensation, proposed bonus, and any proposed reductions or penalties for not completing the protocol.

If the patient satisfactorily completes the following requirements, he or she will receive \$100 total. First, the patient must complete both training modules and all three assessment sessions. Second, this compensation is contingent on the return of the laptop to the lab in working condition without severe damage. If the patient does not return the laptop in reasonable working condition, the patient will not receive compensation for participation in the study.

If the patient completes both training modules within 9 weeks, they will receive a \$25 bonus following their final assessment and return of the laptop.

11. Costs

- a. Detail costs of study procedure(s) or drug (s) or substance(s) to participants and identify who will pay for them.

Each laptop will cost between \$250 to \$300, and each participant's compensation will be between \$100.00 to \$125.00, which will all be paid for by [name]'s Woodrow Wilson Research Fellowship fund. There will be no cost to the patient or to the patient's insurance.

References:

Brackett, M. A., & Mayer, J. D. (2003). Convergent, discriminant, and incremental validity of competing measures of emotional intelligence. *Personality and Social Psychology Bulletin*, 29, 1147-1158.

Friedman PJ. The star cancellation test in acute stroke. *Clinical Rehabilitation*. 1992;6:23–30.

Gur, R. C., Richard, J., Hughe tt, P., Calkins, M. E., Macy, L., Bilker, W. B., ... Gur, R. E. (2010). A cognitive neuroscience-based computerized battery for efficient measurement of individual differences: Standardization and initial construct validation. *Journal of Neuroscience Methods*, 187(2), 254–262. doi:10.1016/j.jneumeth.2009.11.017

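### The statistical argument assumes chronic, non-recovering stroke, but the eligibility list sets no time since onset; the balanced primary contrast is largely protected, while the first-period fallback, the uncontrolled Aim 2 summaries and unequal orders are not

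*Combined protocol and SAP*

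**What the plan says.** Section 5, inclusion criterion 1, requires "Clinical diagnosis of right hemispheric stroke or behavioral variant frontotemporal dementia". None of the five exclusions refers to the onset or phase of stroke; the nearest, exclusion 1, concerns "Prior history of neurological disease affecting the brain other than stroke or frontotemporal dementia". Section 4a makes meeting these criteria a condition of enrolment, with screening by chart review. Time since onset is not among the assessments listed there.

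Two other sections describe a narrower group. Section 4d says "Cognitive rehabilitation for chronic right hemisphere stroke and behavioral variant FTD is very rare". Section 7c says "we expect little change in the Penn CNB with the control (non-specific cognitive exercises) in chronic right hemisphere stroke" and gives the reason: "as we see decline rather than recovery in chronic stroke in these functions".

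The primary outcome in Section 7a is "Change in performance from baseline to 1st post treatment on Penn CNB tasks (Total) vs. 1st post-treatment (new baseline) to 2nd post-treatment". Each period lasts four weeks. The model in Section 7c has subject, treatment and carryover terms, but none for period or time since stroke. Carryover is tested at p < 0.1; if it is significant, only the first-period data are analysed. Section 7d restricts Aim 1 to patients who finish the whole study, but may use those who finish only the social-cognition condition for Aims 2 and 3.

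**The concern.** The eligibility list decides who enters; the rationale does not. As written, it admits patients outside the group for whom Section 7c argues stability. A patient still recovering from a stroke may improve over eight weeks whatever the training. If that improvement slows, it is a period effect, which the written model does not represent.

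At stake are analyses without within-patient protection. The fallback compares different patients, so a mixture of recovering and stable patients widens the spread of the change scores. Before-after summaries for Aim 2 would show recovery as if it were benefit. The pooled contrast is also exposed if attrition, which Section 7c expects to be high, leaves the two orders unequal.

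**Working it through.** **Inputs from the plan (Section 7c).** 13 per group, 26 in total; difference 6 (10 versus 4); two-sided alpha 0.05; power 86%. No SD is given.

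**Assumptions, not in the documents.** A share p = 0.33 of patients is recovering. They gain 6 points in period 1 and 3 in period 2, or 10 then 4, under either training.

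**Step 1: the SD behind 86%.** The figure cannot be checked forward, so I solved for the SD with the noncentral t.
- Two-group t-test, 13 versus 13: SD 4.83.
- Crossover on 26 within-patient differences, 24 df: SD of the difference about 9.65.

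The second reading gives two possible SDs for a first-period change:
- The two change scores share the middle visit. With independent, equal visit errors of variance v, and no patient variation in change, the difference has variance 6v and one change has 2v. Then v = 9.65²/6 = 15.52 and the SD is √31.04 = 5.57.
- If the two change scores are independent instead, the SD is 9.65/√2, about 6.83 before rounding of the inputs.

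I carry 4.83, 5.57 and 6.83 as the range.

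**Step 2: first-period fallback.** Recovery adds variance p(1−p)g², where g is the period 1 gain. For g = 6 this is 0.33 × 0.67 × 36 = 7.96. Power is for 13 versus 13 and a difference of 6.

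| SD without recovery | Power | SD with g = 6 | Power |
|---|---|---|---|
| 4.83 | 86% | √(23.33 + 7.96) = 5.59 | 75% |
| 5.57 | 75% | √(31.02 + 7.96) = 6.24 | 65% |
| 6.83 | 58% | √(46.65 + 7.96) = 7.39 | 51% |

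For g = 10 at SD 5.57, the SD is √(31.02 + 22.11) = 7.29 and power is 52%. Chance imbalance in recovering patients between orders has SD √(0.33 × 0.67 × 2/13) = 0.184, which for g = 6 moves the first-period difference by about 1.1 points (1 SD).

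**Step 3: pooled contrast, balanced 13/13.** Only the drop in gain from period 1 to period 2 matters: 3 or 6 points.
- Drop of 3: SD √(9.65² + 0.2211 × 9) = 9.75, power 85%.
- Drop of 6: SD √(9.65² + 0.2211 × 36) = 10.05, power 83%.

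These remove the mean period difference. If it stays in the residual, as in a model without a period term, the second case gives √(10.05² + (0.33 × 6)²) = 10.25 and about 82%. Simulations with 25-100% of patients recovering, balanced orders and gains of 6 then 3 or 10 then 5 showed average bias near 0 and type I error of 4-5%.

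**Step 4: pooled contrast, unequal completers, no period term.** Bias = (n1 − n2)/N × mean period difference. At 16/10:
- 6 then 3: 6/26 × 0.33 × 3 = 0.23.
- 10 then 4: 6/26 × 0.33 × 6 = 0.46.

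The sign reverses at 10/16. With a period term the bias is 0.

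**Step 5: Aim 2 before-after change.** For patients who completed social-cognition training first and then stopped, recovery contributes on average 0.33 × 6 = 2.0 points (0.33 × 10 = 3.3 in the other scenario) on the Penn CNB scale, with no control change to set against it.

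**The case against.** The strongest reply is that randomised order already deals with this. A reader might infer that spontaneous recovery is mistaken for training benefit in the primary result. The documents do not support that for balanced orders: recovery raises change under both conditions and cancels in the contrast. This part of the reply stands.

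A reader might also infer that recovery would set off the carryover test. Under the standard between-sequence comparison of patient totals, simulated rejection stays at about 10%, so recovery adds noise but no false signal. Only if the carryover term is indexed by period does the rate rise, for example to 20% with half the patients gaining 6 then 3 (SD 6.83). Section 7c defines the index as sequence, though its fallback sentence uses that word where period seems meant. The text does not settle this, so I do not rest the point on it.

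Nor do the documents show that recent strokes will be enrolled. The Abstract's mention of following patients "longitudinally in patients with stroke from the acute stage to approximately one year after stroke" describes the group's other work, not recruitment here. Equally, nothing in the documents establishes how large recovery is or how fast it slows.

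Finally, the plan leans less on stability than Section 7c may suggest. The power calculation allows a control gain of 4, and the fallback applies only after a significant carryover test. Both are fair and limit the severity. They do not remove the mismatch between who is eligible and whom the argument describes.

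**Conclusion.** The inconsistency is established from the text: Sections 4d and 7c describe chronic stroke, and Section 5 does not require it. The consequence for the primary analysis is small: power of about 83-85% instead of 86% with balanced orders, and a shift of about 0.2-0.5 points against a target of 6 at 16/10 completers. That shift comes from the missing period term, and an eligibility edit alone would not cure it whenever a period effect exists. The fallback loses about 7 to 11 percentage points of power under the 6-point assumption and more under 10 points. The Aim 2 summaries can include recovery with nothing to separate it from training. Every size here depends on an assumed share and pace of recovery, and the fallback figures also on an SD the plan does not state. This is worth correcting because it is cheap; it does not invalidate the design.

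**What to change.** 1. Reconcile inclusion criterion 1 with Sections 4d and 7c. The investigators should state the intended stroke phase, and any minimum interval is theirs to set.
2. Record time since onset at entry, from the chart review already planned.
3. If recent strokes are meant to be eligible, remove the chronic-stability argument from Section 7c. Adjust the first-period analysis and other between-patient comparisons for a three-level group: FTD, chronic stroke, recent stroke. Time since stroke cannot serve as a covariate for the whole sample, because it is undefined for FTD.
4. In either case, add an explicit period term to the crossover model.

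The cost is a short amendment, plus slightly slower recruitment if recent strokes must wait, which matters somewhat in a study expecting 20-30 completers from up to 50 enrolled. The alternative costs one or two degrees of freedom for the group covariate. The period term costs one more.

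### Section 7a words the primary outcome as period 1 change versus period 2 change, which conflicts with the social-versus-control contrast used in the rest of the plan

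*Combined protocol and SAP*

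**What the plan says.** Section 7a (Primary outcome variable) reads: "Change in performance from baseline to 1st post treatment on Penn CNB tasks (Total) vs. 1st post-treatment (new baseline) to 2nd post-treatment". It continues with the Penn CNB total and names no training condition.

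The Abstract states the design: "Every participant will engage in both a social-cognitive training condition and a non-specific control training condition in a random order". Section 4a says the starting condition is "randomly determined by selecting one of 30 sealed envelopes"; it does not say how the envelopes divide between the two orders.

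Section 7c opens with a different contrast: "We will compare the change in means of outcome measures after social cognition treatment vs. control treatment". It then restates the endpoint by treatment: "The primary outcome variable will be change in performance on the Penn CNB tasks after the end of each treatment". Its null hypothesis equates a social-cognition mean with a control mean. In its model, the index j "represents the sequence (1 or 2"), yet the same j also indexes the two treatment means and the carryover term. No term is given for period.

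The power paragraph of 7c assumes mean changes of 10 (treatment) and 4 (control). It says: "If the sample size in each treatment group is 13, (a total sample size of 26") and "a crossover design will have 86% power to detect a difference in means of 6". No standard deviation is given.

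**The concern.** Section 7a is the entry headed as the primary outcome, and it sets the first visit interval against the second. With randomised order, that matches social versus control only for participants who had social-cognitive training first. For the others the sign is reversed. The plan therefore carries two descriptions of the primary outcome on the same three visits, and the one in 7a, taken alone, does not address Objective 1.

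An analyst who followed 7a literally and averaged over everyone would estimate how the second interval differs from the first, for example through a larger gain at the first retest or through disease course. Such differences are plausible here: the same tests are given three times in about 8 weeks, and 7c itself anticipates decline in both populations. A constant change per interval would cancel; one that differs between intervals would not.

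**Working it through.** **Inputs from the plan.** Mean change 10 after social-cognitive training and 4 after control; 13 per group, 26 in total; two-sided alpha 0.05; stated power 86% (all Section 7c, Power). The split of orders among completers is not stated, so 13:13 and several unequal splits are shown. Carryover is taken as zero. Let π be any excess of the period 1 change over the period 2 change that is unrelated to treatment.

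**The plan's own figure.** The 86% cannot be reproduced without an SD; it can only be solved backwards. For a 2x2 crossover with 13 per order, analysed by a two-group t-test on within-participant period differences (24 degrees of freedom), the standard error is (SD/2) × √(2/13). Power of 86% for a difference of 6 then implies SD ≈ 9.65 for the within-participant difference. Read as a parallel two-group comparison, it implies SD ≈ 4.83. The 9.65 is used below as an assumption, and only for rejection rates.

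**Step 1: literal 7a, by order.**
- Social first: 10 − 4 + π = +6 + π
- Control first: 4 − 10 + π = −6 + π

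**Step 2: literal 7a, pooled over orders.** Expected value = 6 × (n social-first − n control-first)/N + π.
- 13:13: 6 × 0/26 = 0, plus π
- 14:12: 6 × 2/26 = 0.46, plus π
- 16:10: 6 × 6/26 = 1.38, plus π
- 18:8: 6 × 10/26 = 2.31, plus π

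The assumed effect is 6. What remains at unequal splits reflects the imbalance only. This step needs no SD.

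**Step 3: the same period difference, compared between orders.** [(6 + π) − (−6 + π)]/2 = 6. The full effect is recovered and π cancels.

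**Step 4: rejection rates** (simulation of 40,000 trials, assumed SD 9.65).

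| Split | π | Pooled 7a | Condition contrast, compared between orders |
|---|---|---|---|
| 13:13 | 0 | 2% | 86% |
| 15:11 | 0 | 4% | 85% |
| 18:8 | 0 | 14% | 80% |
| 13:13 | 3 | 22% | 86% |

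The 2% is below 5% because the opposite-signed order means inflate the pooled SD. With no treatment effect, pooled 7a rejects in 33% of trials at π = 3 and in 86% at π = 6.

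**Step 5: is rewording 7a enough?** A social-minus-control difference simply averaged over participants has expectation [n social-first × (6 + π) + n control-first × (6 − π)]/N. At 16:10 this is 6 + (6/26)π = 6 + 0.23π. So 23% of a period effect stays in the estimate unless the model contains a period term.

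**The case against.** The strongest reply is that 7a lists two change scores and names no test. The values 0 and 1.38 appear only after pooling over orders, and nothing in 7c prescribes that. The period difference is also a standard crossover variable; compared between order groups it returns 6 with the period effect removed (Step 3). The power paragraph, with a crossover, 13 per group and a two-group t-test, is compatible with that analysis, although it speaks of treatment groups and not of sequences. Section 7c restates the endpoint by treatment, its null hypothesis is by condition, and nothing ranks 7a above 7c. Section 4b ties each post-treatment visit to the first or second condition, so once the order is known each interval can be mapped to a training type.

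All of this stands. A reader might infer that the trial as planned cannot detect a treatment effect of any size, or that the sponsor will test period against period. The documents support neither inference: both require a pooled test that is not specified, and Objective 1, the hypothesis and the power means point the other way.

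The reply does not make 7a correct. It still names no condition, and the 7c notation does not settle the matter. There j is called sequence, carries the treatment means, and is used like period in the carryover rule, which retains only the first-sequence data as free of carryover. An analyst could code j by period and claim to follow the text.

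**Conclusion.** Wrong as written, moderate severity: the primary endpoint definition in 7a is inconsistent with the contrast the plan intends. Applied literally and pooled over orders, it would have expectation 0 at 13:13 and 1.38 at 16:10 against an assumed effect of 6, plus any difference between periods in full. Those values rest on the plan's means of 10 and 4, no carryover, and pooling. The rejection rates rest in addition on an SD of 9.65 solved back from the stated power, which cannot itself be verified. The inconsistency between 7a and 7c depends on none of these assumptions.

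The missing period term matters in its own right. Balance between orders is not assured: the envelope split is not stated, high attrition is expected, and Aim 1 uses only participants who complete the whole study.

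**What to change.** Reword 7a along these lines: the primary outcome is the within-participant difference between the change in Penn CNB total across the social-cognitive condition and the change across the control condition. Each change is the score at the end of that condition minus the score at its start. The start and end visits follow from the randomised order: baseline and first post-treatment visit for the condition taken first, first and second post-treatment visits for the condition taken second.

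In the 7c model, give treatment and period their own indices, and index sequence/carryover separately from both, so that a period effect does not enter the treatment estimate when the orders are unequal. Use the word sequence only for the order of conditions, and period for the first or second interval, including in the carryover rule. Section 7c already extends a similar analysis to the secondary outcomes, so the same definition can carry over to 7b.

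Cost: one sentence in 7a and one added model term, with one degree of freedom lost. Visits, data collection and sample size do not change.
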